All ordering providers (i.e. APRN's and physicians) in the POD-C pediatric primary care clinic at the Vanderbilt University Medical Center (VUMC) One Hundred Oaks location will be receive an intervention in form of a SIGHT prompted message from a genetic counsellor for each patient meeting criteria (see below). No direct patient interventions will be provided from the study team.

Interventions

Interventions for each group with sufficient detail to allow replication, including how and when they will be administered

Eligible patients will be randomized to the intervention or comparator arm with the intervention arm having a SIGHT predicted score of 0.3 or greater. For patients randomized to the SIGHT- prompted provider message, the clinician responsible for care in that encounter (determined in the usual course of care) will receive a message showing the relevant diagnostic codes contributing to the high score.

Providers screening for or otherwise aware of SIGHT- predicted risk will have full discretion to offer genetic testing and/or refer to genetics providers. The management of screening will follow usual care at VUMC.

Patients will experience usual care until providers screen for the need of genetic testing which they might not otherwise do without the SIGHT-prompted provider message for those identified at highest risk.

11b Criteria for discontinuing or modifying allocated interventions for a given trial participant (eg, drug dose change in response to harms, participant request, or improving/worsening disease)

This protocol presents minimal risks to participants, adverse events or other problems are not anticipated. Risks include discomfort among both providers and patients in discussing the sensitive but important topic of being at risk of genetic disease. The risk model is not perfect and might not identify patients who are at risk – it is not intended to pre-empt providers screening any patient for genetic disease if they choose to do so. The risk model might also identify those not at risk, leading to questions of genetic susceptibility being asked unnecessarily.

Providers may dismiss the SIGHT – prompted provider message and not act on its recommendations at any time. No other intervention is planned. Patients would be unaware of the providers' decisions in that case unless the provider chooses independently to discuss the SIGHT score with them.

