Analysis Metric: Time to event, measured from the initial patient visit to the time genetic testing is conducted.

Method of Aggregation: Median time in days

Specific Measurement Variable: Rates of genetic testing. **Analysis Metric:** Proportion of patients who received testing **Method of Aggregation:** Proportion of patients, presented as a percentage

Time Point: Assessed after one year to include enough time for patients to undergo testing through the usual course of care.

Specific Measurement Variable: Diagnosis via any genetic testing.

Analysis Metric: Proportion of patients diagnosed with a genetic disease following molecular testing or clinical evaluation. **Method of Aggregation:** Proportion of patients, presented as a percentage.

Time Point: Assessed after one year to include enough time for patients to undergo additional testing through usual care.

Specific Measurement Variable: Adherence to the SIGHT-prompted provider message.

Analysis Metric: Frequency of provider actions via referral to genetics and ordering a patient CMA following receipt of a SIGHT-prompted message.

Method of Aggregation: Proportion of instances where the provider follows the SIGHT recommendation.

Time Point: Information will be collected at the end of the study.

Participant timeline

- Time schedule of enrolment, interventions (including any run-ins and washouts), assessments, and visits for participants. A schematic diagram is highly recommended (see Figure)
 - 1. Enrollment Process: Eligibility Screening: Conducted at the initial patient visit. Consent Process: Following eligibility screening, informed consent will not be obtained as patients are following usual care.
 - **2. Interventions:** SIGHT-Prompted Provider Message: Initiated following screening for patients who meet the predefined risk threshold.
 - 3. Assessments: Baseline Assessment: Conducted during the initial visit, including collection of patient health data. Follow-up Assessments: Scheduled after initial visit to monitor the outcomes, such as number of patients receiving a diagnosis, time to genetic testing, and diagnostic yield.
 - 4. Visits: Initial Visit: SIGHT prompted provider message followed by review of referrals and documentation attributable to the initial patient visit. Subsequent Visits: Regular follow-ups as per usual pediatric care, during which recommendations and any genetic testing decisions are documented and assessed.

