The allocation will be done with a 1:1 ratio. This randomization process is designed to ensure that patients surpassing a previously defined threshold for predicted risk of needing genetic testing are randomly selected for the intervention group. A SIGHT-prompted provider message will be generated for patients in the intervention group, while patients in the control group will receive usual care without this prompted message.

Patients who exceed a predefined risk threshold and are scheduled for their first visit within a year will be eligible for randomization to the intervention group. An estimated 500 patients will be randomly selected to receive a SIGHT-prompted provider message as part of the intervention.

The comparator arm will consist of the random eligible patients who do not receive the intervention. These patients will not be a typical control group to avoid ethical concerns related to withholding potentially important care but will follow usual care and may still get genetic testing.

To maintain the integrity of the randomization process, the study will employ random allocation to intervention and comparator arms with the expectation of a 1:1 ratio over time.

This method of randomization aligns with ethical standards and the goal of the study to evaluate the effectiveness of the SIGHT intervention while ensuring that all patients receive the usual care appropriate to their clinical needs. Allocation concealment mechanism

Mechanism of implementing the allocation sequence (eg, central telephone; sequentially numbered, opaque, sealed envelopes), describing any steps to conceal the sequence until interventions are assigned.

The allocation sequence will be implemented using a secure, computerized system to ensure allocation concealment. This system will generate the allocation sequence and assign patients who surpass the predefined risk threshold to either the intervention or the comparator group.

The allocation system will maintain concealment by ensuring that randomization is not processed until a patient has been identified as eligible. This process occurs after the patient's eligibility is confirmed but before any intervention is assigned, to prevent selection bias and to maintain the integrity of the randomization process.

Implementation 16c

Who will generate the allocation sequence, who will enrol participants, and who will assign participants to interventions

Allocation Sequence Generation

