c. Diagnosis via any test (molecular confirmation)	More patients will receive a diagnosis from molecular confirmation outside of firs tier testing via a CMA.	Number of patients flagged by SIGHT who receive a diagnosis via any test over one year vs controls [binary]	Chi-square test
d. Adherence to Intervention	Providers who Receive SIGHT prompts demonstrate higher adherence recommendations compared to controls	Proportion of eligible patients where providers ordered a CMA and place genetics referrals after receiving a prompt [binary]	Chi-square test; logistic regression adjusting for covariates

20b Methods for any additional analyses (eg, subgroup and adjusted analyses)

Subgroup analysis within demographic groups (sex, race, age) will be performed as described in the primary analysis but within each group or stratified by age.

Definition of analysis population relating to protocol nonadherence (eg, as randomised analysis), and any statistical methods to handle missing data (eg, multiple imputation)

Non-adherence and missing data for the SIGHT protocol are non-applicable in this context as patients will follow usual care. Patients who are lost to follow up or have no follow up care during the duration of the study will remain included in the analysis.

Methods: Monitoring

Data monitoring 21a

Composition of data monitoring committee (DMC); summary of its role and reporting structure; statement of whether it is independent from the sponsor and competing interests; and reference to where further details about its charter can be found, if not in the protocol. Alternatively, an explanation of why a DMC is not needed.

This study does not require a DMC as the protocol presents minimal risks to participants and adverse events or other problems are not anticipated. In the unlikely event that such events occur, unanticipated problems involving risks to subjects or others will be reported immediately to the PI and and within 7 days of the PI's notification of the event to the IRB.

21b Description of any interim analyses and stopping guidelines, including who will have access to these interim results and make the final decision to terminate the trial

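### Row d conditions adherence on a prompt that controls never get, yet tests it against controls; and its methods ignore the clinician, so limits for messaged-arm adherence would be too narrow beyond this clinic's providers

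*Protocol*

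**What the plan says.** Row d of the Section 20a table defines the adherence outcome as "Proportion of eligible patients where providers ordered a CMA and place genetics referrals after receiving a prompt [binary". Its hypothesis is "Providers who Receive SIGHT prompts demonstrate higher adherence recommendations compared to controls", and its method is "Chi-square test; logistic regression adjusting for covariates". The text of Section 20a also assigns the chi-square test to provider adherence. Its covariate examples, given for subgroups, are patient age, sex and race. No clinician term or clustered variance is named.

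Section 12 summarises the same outcome differently, as a single proportion with no comparator: "Proportion of instances where the provider follows the SIGHT recommendation".

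On who acts, Section 11a says that "the clinician responsible for care in that encounter (determined in the usual course of care) will receive a message". The recipients are "All ordering providers (i.e. APRN's and physicians) in the POD-C pediatric primary care clinic", who are to get a "SIGHT prompted message from a genetic counsellor for each patient meeting criteria". Section 16c leaves the response wholly to the provider. On volume, Section 16a states: "An estimated 500 patients will be randomly selected to receive a SIGHT-prompted provider message as part of the intervention". Randomisation is by patient within the one clinic, so a clinician can have patients in both arms. Section 18a lists CMA orders, genetics referrals and dates for extraction, but not the clinician who received the message.

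**The concern.** There are two linked problems.

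First, row d contradicts itself. An event that requires a prompt cannot occur in an arm without prompts. Read literally, the control proportion is zero by construction and the test is empty. Read loosely, the outcome is CMA ordering plus referral in both arms, which measures the effect of the message and is not adherence to it.

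Second, on the Section 12 reading, each observation is one clinician's decision, repeated over many messages during a recruitment period of two to three years. Some clinicians may act on most messages and others on few. Section 11c itself distinguishes physicians who give constant care from those with interim appointments. A chi-square test or a plain logistic model counts each message as a separate piece of information.

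Adherence matters because it tells a reader whether a null trial means that the model failed or that the message was ignored, and it is what another clinic would look at before adopting SIGHT. An interval labelled 95% that covers far less would mislead on that question.

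**Working it through.** **The plan's own figure.** The protocol states no precision or power for adherence. Its only calculation is for the primary outcome (Section 14: 0.81% versus 3.6%, 80% power, 500 per arm). The two-proportion formula gives 434 per arm without and 503 with continuity correction, so 500 is reproduced. It has no bearing on row d.

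**Inputs for adherence.** The number of messages, n = 500, is from Section 16a. The rest is assumed, because the protocol does not give it: number of clinicians k = 15 to 40, intraclass correlation (ICC) 0.05 to 0.20, adherence 40%, and equal messages per clinician.

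**Messaged-arm proportion.**
- Half-width under independence: 1.96 × √(0.4 × 0.6 / 500) = 4.3 points.
- Design effect: DEFF = 1 + (500/k − 1) × ICC.
- Clustered half-width: 4.3 × √DEFF.
- Actual coverage of the independence interval: 2Φ(1.96/√DEFF) − 1.

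| k | ICC | DEFF | Half-width (points) | Coverage of nominal 95% |
|---|---|---|---|---|
| 40 | 0.05 | 1 + 11.5 × 0.05 = 1.58 | 5.4 | 88% |
| 20 | 0.10 | 1 + 24 × 0.10 = 3.40 | 7.9 | 71% |
| 15 | 0.20 | 1 + 32.3 × 0.20 = 7.47 | 11.7 | 53% |

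A beta-binomial simulation (1000 patients randomised 1:1 individually, 4000 replicates per setting) agrees: about 70% coverage at k = 20 and ICC 0.10, and 86% to 88% at k = 40 and ICC 0.05. With wider assumptions (10 to 50 clinicians, ICC 0.02 to 0.20), DEFF runs from 1.18 to 10.8, so the correct interval is 1.09 to 3.29 times as wide.

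**Between-arm comparison**, with CMA order plus referral counted the same way in both arms:
- *No message effect, clinicians differing in their ordering habits.* With 10, 20 or 40 clinicians and ICC 0 to 0.20, the chi-square rejected in 4.2% to 5.6% of replicates. Coverage of the difference was about 95%. A clinician's habit enters both arms and cancels.
- *Clinicians differing in their response to the message, extreme case* (a clinician's rates in the two arms unrelated). With 20 clinicians, coverage of the difference fell to about 80% (ICC 0.05) and 71% (ICC 0.10).
- *A milder case*, with each clinician's rates correlated across arms (9% versus 40%, 20 to 50 clinicians, ICC 0.05 to 0.10). Coverage was 91% to 95%.

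**Fixed set of clinicians.** If the target is only this clinic's present providers and their share of messages, the spread between clinicians is not sampling error. The variance is then [p(1 − p) − between-clinician variance]/n, no larger than the naive value. At ICC 0.10 the half-width would be 4.3 × √0.9 = 4.1 points.

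**The case against.** The strongest case on the other side is that row d is written as a comparison with controls, that clinicians are crossed with arm, and that the named chi-square is valid for that comparison. This stands. A reader might infer that all of row d's p-values and limits are too small. The documents do not support that: under no message effect the test holds its level, and the interval for the difference falls short only if clinicians respond differently to the message and the result is generalised beyond them.

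A reader might also infer that clinician-level predictors would appear significant by chance. The protocol plans no such predictor; its named examples are patient characteristics.

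It can further be said that the protocol states no confidence interval for the adherence proportion, that covariate lists and variance estimators are commonly left to an analysis plan, which is not at hand, and that the number of clinicians and the ICC are unknown. Each is true. The size is therefore an assumed range, and the interval argument is conditional on limits being reported. Adherence is also the last-listed secondary outcome and is absent from the key secondary outcomes in the registration table at the end of the protocol.

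What these points do not remove is the clash between outcome and hypothesis in row d, which is in the protocol's own text. Nor do they change the fact that the methods it names for adherence make no provision for the clinician.

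**Conclusion.** The point holds in limited form. Row d mixes two quantities and must be reconciled before any variance question can be settled. For the messaged-arm proportion, independence-based limits are too narrow if they are meant to apply beyond the present providers: a half-width of 5.4 to 11.7 points instead of 4.3, under the assumed 15 to 40 clinicians, ICC 0.05 to 0.20 and 40% adherence. Unequal message counts per clinician would tend to widen this further. For inference confined to this clinic's providers there is no understatement. The between-arm chi-square is sound as a test of no message effect. The primary outcome and the sample size are unaffected.

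**What to change.** Split row d in two.

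1. **Messaged-arm adherence.** The proportion of messages followed by a CMA order and a genetics referral, reported with a clinician-clustered 95% interval and a display of the spread across clinicians. No control comparison.
2. **Between-arm comparison.** CMA order plus genetics referral, defined identically in both arms from the index visit over a stated window. Keep the chi-square test. Fit the logistic model with a random clinician intercept, or by GEE with a small-sample robust variance clustered on clinician. A random intercept alone allows for differing habits but not for differing response to the message; if the result is to be generalised, use GEE or add a clinician-specific arm effect.

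Record the encounter clinician's code for every randomised patient in both arms, add it to the data listed in Section 18a, and align the Section 12 entry with the two parts.

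The cost is one extra data field, a few lines of analysis and a wider interval on one secondary outcome. No extra patients are needed and the primary analysis does not change.

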 - **5. Study Close-Out:** Final Assessment: Conducted at the end of the study period to collect the final data on all outcomes.

Sample size

14 Estimated number of participants needed to achieve study objectives and how it was determined, including clinical and statistical assumptions supporting any sample size calculations

Previous data suggest that, under the usual course of care, 9% of high-risk patients (those with a predicted score of ≥ 0.3) had genetic testing. Of those, 9% received a genetic diagnosis, resulting in a genetic diagnosis rate of 0.81% (0.09*0.09) among high-risk patients

One thousand high-risk patients (score \geq 0.3) will be randomized 1:1 (500 per arm). This sample size provides 80% power to detect an increase in the genetic diagnosis rate from 0.81% under standard care to at least 3.6% with the SIGHT intervention (chi-square test, α =0.05)

Recruitment 15 Strategies for achieving adequate participant enrolment to reach target sample size

The VUMC POD-C pediatric clinic has had over 200,000 patient encounters from over the last five years with more than 30,000 unique patients and over 10,000 unique patients in 2023. The clinic averages 144 visits per day (median = 165). Estimates indicate potentially 1-2 patients flagged per day which should readily provide enough patients for an adequate sample size over a two to three-year period.

Methods: Assignment of interventions (for controlled trials)

Allocation: Sequence generation 16a

Method of generating the allocation sequence (eg, computer-generated random numbers), and list of any factors for stratification. To reduce predictability of a random sequence, details of any planned restriction (eg, blocking) should be provided in a separate document that is unavailable to those who enrol participants or assign interventions.

The SIGHT study will utilize a computer-generated assignment schedule for all patients seen in the POD-C pediatric clinic with a score greater than or equal to 0.3 for allocation into the intervention group. A computer-generated randomization schedule will be used for assigning participants to the control group. This is completed using the built-in random module of python, assigning patients with equal scores either 0 (control) or 1 (intervention) to each patient who has met all previously defined criteria, with assignments saved to a log file.

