A sample size re-estimation will be conducted after 250 patients have been randomized to account for uncertainty, and adherence rates for the initial test-referral rate used in the sample size calculation. An independent analyst, who will be blinded to the randomization assignment, will calculate the observed test-referral rate across all patients. This analysis will focus on updating the test-referral rate parameter to ensure the study is adequately powered. The updated test-referral rate will be used to reassess and, if necessary, adjust the total sample size to maintain the study's power at 80%. This process will ensure the trial remains robust and capable of detecting meaningful differences between the usual care and SIGHT-guided intervention arms.

17b If blinded, circumstances under which unblinding is permissible, and procedure for revealing a participant's allocated intervention during the trial

NA

Methods: Data collection, management, and analysis

Data collection methods

18a

Plans for assessment and collection of outcome, baseline, and other trial data, including any related processes to promote data quality (eg, duplicate measurements, training of assessors) and a description of study instruments (eg, questionnaires, laboratory tests) along with their reliability and validity, if known. Reference to where data collection forms can be found, if not in the protocol

The trial will utilize the SIGHT predictive model to generate a score for all POD-C patients. Data collection will include baseline and outcome data assessed via EHR data queries for internal genetic test orders in form of a CMA, referrals to pediatric genetics, and attributable dates. All queried metrics and additional metrics related to genetic testing results will be assessed and verified through chart review performed by a clinician (genetic counselor or geneticist) for the intervention and comparator arm for patients seen in the POD-C clinic. The validity and reliability of the SIGHT predictive model, as well as the data collection methods, have been ensured through pilot testing and chart review prior to study implementation. All data collected and related documentation will be available in the trial master file with data availability based upon institutional policy.

Plans to promote participant retention and complete followup, including list of any outcome data to be collected for participants who discontinue or deviate from intervention protocols

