The statistical analysis will utilize a chi-square test for binary outcomes such as the presence or absence of a genetic diagnosis as identified by the test or provider adherence to SIGHT message recommendations. For continuous secondary outcomes, such as the time to genetic testing, a T-test or Mann-Whitney U test will be used depending on data distribution. Subgroup analyses will involve regression methods to assess the differential effects of the intervention across subgroups defined by baseline demographic characteristics (e.g. age, sex, race). Multivariate analyses will be conducted using logistic regression for binary outcomes and linear or Cox proportional hazards regression for continuous or time-to-event outcomes, respectively. Model assumptions will be checked through the assessment of residuals and model fit will be evaluated accordingly.

When indicated, a two-sided p-value of less than 0.05 will be considered statistically significant. The Bonferroni correction will be applied to account for multiple comparisons when analyzing multiple outcomes. R will be used to perform all analyses. The analysis plan will follow the intention-to-treat principle, with all randomized participants included in the analysis according to the group to which they were allocated.

Variable/outcome	Hypothesis	Outcome measure	Methods of analysis
Primary			R will be used to perform all analysis.
Number of diagnoses via CMA	More patients are diagnosed being flagged by SIGHT via a Chromosomal Microarray	Number of patients flagged by SIGHT who receive a diagnosis via CMA over one year vs controls [binary]	Chi-square test
Secondary			
a. Time to genetic test	Patients in the intervention arm will receive genetic testing faster than those in the controlarm.	Duration in days for which patients flagged by SIGHT receive a genetic test vs control [continuous]	Cox proportional Hazards to compare the time to event (in this case genetic testing) between two groups while controlling for covariates.
b. Rates of genetic testing	Increased rates of genetic testing in the intervention arm	Rates of genetic testing ordered by providers between cases and controls over a one-year period after POD-C visit [continuous'	Binary logistic regression to calculate the odds ratio for the likelihood of receiving a genetic test in the intervention arm compared to the controls

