As stated in item 21a the SIGHT study will not have a DCM but rather report all outcomes to the IRB. Given that the study maintains low risk for patient harm, stoppage of the study is not anticipated but in the event of unforeseen circumstances the PI has full authority to end the study. An interim analysis for sample size re-estimation will be conducted after approximately 250 patients have been enrolled to refine the test-referral rate and ensure the study is adequately powered. An independent analyst, blinded to arm assignment, will perform this recalculation. This is not an efficacy or early-stopping analysis but a parameter update.

Harms

22 Plans for collecting, assessing, reporting, and managing solicited and spontaneously reported adverse events and other unintended effects of trial interventions or trial conduct

This protocol presents minimal risks to participants and adverse events, or other problems are not anticipated. Risks include discomfort among both providers and patients in discussing the sensitive but important topic of being at risk of genetic disease. The risk model is not perfect and might not identify risk in those who are at risk – it is not intended to pre-empt providers screening any patient (or all patients) for genetic disease if they choose to do so. The risk model might also identify risk in those not at risk, leading to questions of genetic susceptibility being asked unnecessarily.

Reporting of Adverse Events or Unanticipated Problems involving Risk to Participants or Others

The study coordinator, with PI oversight, is responsible for ensuring protocol compliance, data integrity, and participant safety. This protocol presents minimal risks to participants and adverse events, or other problems are not anticipated. In the unlikely event that such events occur, unanticipated problems involving risks to subjects or others will be reported immediately to the PI, and in writing within 7 days to the IRB. The PI will apprise fellow investigators and study personnel of all adverse events that occur during the conduct of this research project through regular study meetings. Annual reports will be submitted to the IRB summarizing study progress, adverse events, complaints about the research, and any protocol violations.

Auditing 23 Frequency and procedures for auditing trial conduct, if any, and whether the process will be independent from investigators and the sponsor

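### The sample size re-estimation in items 17a and 21b does not say which effect is held fixed, how the pooled rate is split by arm, or whether N may fall below 1000, so it cannot ensure power

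*Protocol*

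**What the plan says.** Item 14 (Sample size) builds the usual-care diagnosis rate from two inputs: "9% of high-risk patients (those with a predicted score of ≥ 0.3) had genetic testing", and "Of those, 9% received a genetic diagnosis". Their product is 0.81%. The intervention rate is not built this way. It appears only as an absolute target, an increase "from 0.81% under standard care to at least 3.6% with the SIGHT intervention", with 500 patients per arm, 80% power and "chi-square test, α =0.05". Item 20a makes the 5% level two-sided.

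Item 17a (Blinding) adds a re-estimation after 250 randomized patients. An analyst blinded to arm computes the test-referral rate over all patients, and "The updated test-referral rate will be used to reassess and, if necessary, adjust the total sample size" so that power stays at 80%. Item 21b (Interim analyses) gives the purpose as "to refine the test-referral rate and ensure the study is adequately powered" and describes the step as a parameter update, not an efficacy or early-stopping analysis.

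Neither item says what happens to the 3.6% when the control rate moves, how a pooled rate becomes a rate for each arm, or whether N has a minimum.

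**The concern.** The testing rate enters the item 14 calculation only through the control rate. If it is updated and the 3.6% target is left alone, a lower testing rate widens the assumed difference and reduces N, at the moment when diagnoses are turning out rarer. If the ratio of the two rates is kept instead, the same observation raises N. Both readings fit the text, and they move the trial in opposite directions.

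As written, the choice could be made once the pooled rate is known. Blinding the analyst to arm does not prevent that, because the choice depends on the pooled rate and not on the arm results.

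A second gap comes before this one. Item 14 uses a usual-care testing rate, while the interim produces a rate over both arms. If the message works as planned, the two differ widely.

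**Working it through.** **Inputs from item 14.** Usual-care testing 9%, yield 9%, control rate 0.09 × 0.09 = 0.81%, target 3.6%, 500 per arm. The difference is 3.6 − 0.81 = 2.79 points and the ratio is 3.6/0.81 = 4.44. Two-sided 5% level, 80% power.

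**Formula, per arm.** With p̄ the mean of p₁ and p₂:

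n₀ = [1.96·√(2p̄(1−p̄)) + 0.8416·√(p₁(1−p₁) + p₂(1−p₂))]² / (p₂−p₁)²

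Continuity-corrected: n = (n₀/4)·[1 + √(1 + 4/(n₀·(p₂−p₁)))]²

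**Reproducing item 14.** For 0.0081 against 0.036, p̄ = 0.02205 and n₀ = (0.407 + 0.174)²/0.0279² ≈ 434. The correction gives n = (434/4)·(1 + √1.331)² ≈ 503 per arm, 1006 in total, against the stated 500 and 1000. The plan's figure is therefore reproduced with the continuity correction. Without it the total is 867.

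**Changing the usual-care testing rate.** The control rate is the testing rate × 0.09. The 6% and 13% rates are illustrative. Entries are total N, corrected, as twice the unrounded per-arm figure.

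| Testing rate | Control rate | 3.6% kept | 2.79 points kept | Ratio 4.44 kept |
|---|---|---|---|---|
| 6% | 0.54% | 803 | 901 | 1519 |
| 9% | 0.81% | 1006 | 1006 | 1006 |
| 13% | 1.17% | 1395 | 1145 | 689 |

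At 6% the uncorrected totals are 677 (target), 763 (difference) and 1312 (ratio), the same pattern.

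**Power after a cut to 402 per arm (testing 6%).** Exact binomial power of the chi-square test, corrected (uncorrected):

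- 0.54% against 3.6%, 402 per arm: 85% (90%).
- 0.54% against 2.4% (ratio kept, 4.44 × 0.54%), 402 per arm: 50% (60%).
- 0.54% against 2.4%, 500 per arm: 61% (71%).

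The 2.4% rate is not stated in the protocol. It is what the item 14 ratio gives at 6% testing.

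**Pooled rate.** Assume that the 9% yield also holds in the intervention arm; the protocol gives it for usual care only. Then 3.6% requires 3.6/9 = 40% testing in that arm, and the planned pooled rate is (9 + 40)/2 = 24.5%. Entered directly as the control testing rate, it gives a control diagnosis rate of 0.245 × 0.09 = 2.205%. Corrected total N is then about 4830 with the 3.6% target kept, and about 355 with the ratio kept (2.205% against 9.8%). In this example the trial is going exactly to plan, so neither figure is usable.

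**The case against.** **The detail belongs in the SAP.** The protocol gives the timing, the parameter, the power and the blinded analyst, and the algorithm may sit in a document not shown. That carries weight for routine detail. It does not cover this case, because the protocol itself promises adequate power from updating one parameter, and what it leaves open decides the sign of the change.

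**The smaller trial is not underpowered for its target.** This stands. A reader might infer that the rule leaves the trial short of power for 3.6%. It does not: at 402 per arm the power for 0.54% against 3.6% is 85% (90% uncorrected). The 50% applies to an effect the protocol never states. The loss arises only if the intervention rate falls with testing. The protocol's testing-times-yield logic points that way, since at 9% yield 3.6% needs 40% testing in the intervention arm, but no passage says so.

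**Sampling error.** A reader might also infer that chance among 250 patients around a 9% rate makes a cut likely. The documents do not support that. The rate is pooled over both arms and would be near 9% only if the message changed nothing.

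**Other readings and safeguards.** Item 17a also mentions adherence. If the updated rate were meant to feed both arms, a lower rate would raise N; this is one more reading the text leaves open. The Protocol amendments section requires ethics approval for changes in design, which would plausibly cover a change in N. That is approval of a decision, not a rule for making it.

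**Conclusion.** The point holds as a defect in a stated rule. Items 17a and 21b fix the parameter and the power but not the effect, the conversion from pooled to arm-specific rates, or a floor. At an illustrative 6% usual-care testing rate, permissible readings run from about 803 to about 1519 patients, so the step cannot be said to ensure adequate power.

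The potential loss is moderate and conditional. If the ratio stays at 4.44, cutting to 402 per arm costs about 11 points of power compared with 500 per arm, with or without the continuity correction. If 3.6% is still achieved, nothing is lost. The conclusion that the direction is undetermined does not depend on the correction. The pooled-rate figures rest on a 9% yield in the intervention arm, which is an assumption.

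This should be corrected before the interim. It does not undermine the item 14 calculation, which reproduces.

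**What to change.** In items 17a and 21b, before the interim takes place:

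1. Name the effect held fixed in the recalculation, for example the item 14 ratio of 4.44, the 2.79-point difference or the 3.6% target.
2. State how the blinded pooled rate is converted to a testing rate for each arm. Naming the effect alone is not enough: with the ratio kept and 24.5% entered as usual care, N would be about 355.
3. State that the re-estimation never sets N below the planned 1000.
4. If the recalculated N cannot be reached, report the power that 1000 patients give instead of saying that 80% is ensured.

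The cost is a few sentences and no patients beyond the planned 1000. The downside is that the option to stop recruitment below 1000 when the observed rate looks favourable is lost.
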